5.2. Planned Dosage and Duration of Treatment

5.2.1. Dosage and Administration

Florbetapir F 18:

Subjects will receive a single IV bolus administration target dose of 370 MBq (10 mCi) of Florbetapir F 18 Injection.

¹⁸F-AV-1451:

All subjects will receive a single IV bolus administration target dose of 370 MBq (10 mCi) of ¹⁸F-AV-1451 Injection.

5.2.2. Rationale for Dosages

This trial is designed to evaluate the brain tau protein imaging properties and safety of ¹⁸F-AV-1451 to be used in subjects with cognitive impairment and healthy volunteers. ¹⁸F-AV-1451 will be administered IV in a radioactive target dose of 370 MBq with a maximum human mass dose (MHD) limited to 20 µg of compound by weight. This dose is 150 fold lower than the NOAEL observed in the rat single dose toxicity study and is 50 fold lower than the NOAEL observed in the rat and dog repeat dose toxicity studies.

Human dosimetry has been obtained in nine subjects. The results estimated an Effective Dose of 8.92 mSv for an anticipated 370 MBq (10 mCi) injection and is comparable to the effective dose of approved ¹⁸F-labeled compounds such as FDG and Florbetapir F 18 Injection.

The proposed dose has been shown to have acceptable image quality in preliminary human studies. No treatment related adverse events have been reported using this regimen.

5.3. Selection of Subjects**5.3.1. Inclusion Criteria**

Subjects who meet all of the following criteria are eligible to enroll in this trial as cognitively healthy volunteers:

1. Male or female subjects ≥ 20 to ≤ 40 years of age
(n = approximately 20)
-OR-
Male or female subjects ≥ 50 years of age
(n = approximately 60)
2. MMSE ≥ 29
3. No significant history of cognitive impairment
4. Can tolerate PET imaging procedures
5. Can tolerate MRI scan procedures, and
6. Subjects who signed an IRB approved informed consent prior to any study procedures.

Subjects who meet all of the following criteria are eligible to enroll in the arm of this trial reserved for patients with MCI:

1. Male or female subjects ≥ 50 years of age

2. MMSE ≥ 24
3. Have MCI consistent with NIA-Alzheimer's Association working group's diagnostic guidelines for AD: Alzheimer's Dementia 7:270-9, 2011 (Albert 2011), including the following:
 - a. Have cognitive decline verified by the study physician.
 - b. Evidence of objective impairment in one or more cognitive domains, with supporting evidence from objective testing if available,
 - c. Preservation of independence in functional abilities,
 - d. Not demented
4. Have a study partner who has significant interaction with the subject and can report on the subject's activities of daily living
5. Can tolerate PET imaging procedures
6. Can tolerate MRI scan procedures, and
7. Ability to provide informed consent for study procedures (If the patient is ineligible to give informed consent, based on local standards, the patient's legal representative may consent on behalf of the patient but the patient must still confirm assent. This person may serve as the study partner as well).

Subjects who meet all of the following criteria are eligible to enroll in the arm of this trial reserved for patients with AD:

1. Male or female subjects ≥ 50 years of age
2. MMSE > 10
 - a. Approximately 60 subjects with an MMSE ≥ 20
 - b. Approximately 10 subjects with an MMSE > 10 and < 20
3. Subjects with possible or probable AD based on the NIA-Alzheimer's Association working group's diagnostic guidelines for AD: Alzheimer's Dementia 7:263-9, 2011
4. Have a study partner who has significant interaction with the subject and can report on the subject's activities of daily living
5. Can tolerate PET imaging procedures
6. Can tolerate MRI scan procedures, and
7. Ability to provide informed consent for study procedures (If the patient is ineligible to give informed consent, based on local standards, the patient's legal representative may consent on behalf of the patient but the patient must still confirm assent. This person may serve as the study partner as well).

Subjects who meet all of the following criteria are eligible to enroll in the second phase of this trial: Confirmatory Cohort:

1. Male or female subjects ≥ 50 years of age (n = approximately 150)

2. Cognitively impaired subjects (MCI or dementia with a suspected neurodegenerative cause) with an MMSE ≥ 20 and ≤ 27 . (For the purpose of ensuring a distribution of disease severity, a target of at least 1/3 of the enrolled subjects will have dementia).
3. Have a study partner who has significant interaction with the subject and can report on the subject's activities of daily living
4. Can tolerate PET imaging procedures
5. Can tolerate MRI scan procedures, and
6. Ability to provide informed consent for study procedures (If the patient is ineligible to give informed consent, based on local standards, the patient's legal representative may consent on behalf of the patient but the patient must still confirm assent. This person may serve as the study partner as well).

5.3.2. Exclusion Criteria

Subjects will be excluded from enrollment if they:

1. Have current clinically significant psychiatric disease. Subjects with behavior dysfunction in AD may be entered only after discussion and with approval of the sponsor. The investigator should carefully consider whether subjects with behavior dysfunction in AD will be able to complete the imaging session
2. Have evidence of structural abnormalities such as major stroke or mass on MRI that is likely to interfere with interpretation of a PET scan on MRI
3. Have a history of moderate or severe traumatic brain injury (TBI) by OSU TBI-ID method or evidence of brain injury by MRI or CT imaging
4. Are claustrophobic or otherwise unable to tolerate the imaging procedure
5. Have current clinically significant cardiovascular disease or clinically significant abnormalities on screening ECG (including but not limited to Fridericia's corrected QT (QTcF) >450 msec)
6. A history of additional risk factors for Torsades de Pointes (TdP) (e.g., heart failure, hypokalemia, family history of Long QT syndrome) or are taking drugs that are known to cause QT-prolongation (a list of prohibited and discouraged medications is provided by the Sponsor)
7. Have a current clinically significant infectious disease, endocrine or metabolic disease, pulmonary, renal or hepatic impairment, or cancer that the investigator believes would affect study participation or scan results
8. Have a history of significant or ongoing alcohol abuse or substance abuse or dependence
9. Are females of childbearing potential who are not surgically sterile, not refraining from sexual activity or not using reliable methods of contraception. Females of childbearing potential must not be pregnant (negative serum β -HCG at the time of screening and negative urine β -HCG within 24 hours prior to injection) or

breastfeeding at screening. Females must agree to avoid becoming pregnant, and both females and males must agree to refrain from sexual activity or to use reliable contraceptive methods for 90 days following administration of ¹⁸F-AV-1451 Injection

10. Have had a non-study related radiopharmaceutical imaging or treatment procedure within 7 days prior to the ¹⁸F-AV-1451 or florbetapir F18 imaging session
11. Are receiving any investigational medications, or have participated in a trial with investigational medications within the last 30 days
12. In the opinion of the investigator, are otherwise unsuitable for a study of this type.

5.4. Prior and Concomitant Therapy

Except as noted below, all medications (prescription or over-the-counter) that have been started prior to screening may be continued during the course of the trial. All medications that are continued from the start of the trial or that are started during the trial (other than the study medication) must be documented in the case record form on the Concomitant Medication Page of the Case Record Form (CRF).

Investigators must discuss with the sponsor and carefully consider whether subjects requiring psychotropic medications will be able to complete the imaging session.

Subjects who are taking drugs that are known to cause QT-prolongation may not be enrolled in the study (a list of prohibited and discouraged medications is provided by the Sponsor).

Subjects may be permitted to enroll in a clinical trial with a potential disease modifying (anti-tau or anti-amyloid) investigational medication after discussion with the sponsor.

5.5. Removal of Subjects from Trial

Subjects must be removed from the trial if:

1. Informed consent is withdrawn; or
2. The investigator or the sponsor believes it is in the best interest of the subject to be removed from the trial.

Subjects may be withdrawn from the trial if a serious adverse event occurs. The date and reason for discontinuation should be noted on the CRF. Subjects who discontinue prematurely should be seen for a final evaluation.

5.6. Premature Termination of Trial/Closure of Center

The sponsor may discontinue the trial at any time. Reasons for discontinuation of the trial may include, but are not limited to, new information on safety or efficacy, requests from regulatory authorities, or changes in business priorities. Additional reasons for center closure may include, but are not limited to, excessive protocol violations, inadequate regard for subject safety, failure to follow recommended procedures (e.g., documentation), failure or inability to accommodate Avid/CRO monitors or to provide

required access to data and source documents, staff turnover or inadequate staffing, and inadequate enrollment. Except in cases affecting subject safety, the investigators will be given a minimum of 30 days to complete final study evaluations for ongoing subjects. In all cases of center or study termination, appropriate steps will be taken to ensure the safety of study subjects.

6. WARNINGS/PRECAUTIONS

The most up-to-date and complete information regarding the use of ¹⁸F-AV-1451 Injection can be found in the investigator's brochure.

In brief, ¹⁸F-AV-1451 Injection is an experimental imaging agent that will be used at relatively low (tracer) doses. However, because relatively little toxicological evaluation has been completed, and because ¹⁸F-AV-1451 Injection is in the early stages of clinical investigation, it is recommended that subjects receiving ¹⁸F-AV-1451 Injection be followed closely by means of adverse event reporting, vital signs, ECGs, and laboratory tests.

There are no data on the effects of ¹⁸F-AV-1451 Injection in human perinatal development. For this reason, females must avoid becoming pregnant. Both females and males must use adequate contraceptive methods for 90 days after administration of ¹⁸F-AV-1451 Injection. ¹⁸F-AV-1451 Injection must not be administered to females who are pregnant or lactating.

7. PROCEDURES AND METHODS

7.1. Assessment Periods

See Section 11.2, Trial Flow Charts.

This study will be comprised of a cross-sectional component and a longitudinal component. Subjects in both the Exploratory Phase and Confirmatory Phase will have screening visit(s), a florbetapir F 18 PET imaging visit, a ¹⁸F-AV-1451 PET imaging visit, and follow-up phone calls after each imaging visit. Subjects who are ≥ 50 years old will return for follow-up visits at 9 (+/-2) and 18 (+/-2) months following the initial ¹⁸F-AV-1451 scan. Cognitive assessments and updates to concomitant medications and medical history will be collected at each follow-up visit. Subjects in the Exploratory Phase will also have follow-up ¹⁸F-AV-1451 scans and MRI.

7.1.1. Screening and Baseline Visit:

Screening may take place over several days. All screening assessments should be performed within 30 days of the initial ¹⁸F-AV-1451 PET imaging session.

Screening assessments will include:

- Informed consent;

- Demographics (age, gender, race, ethnicity, education, alcohol, drug use, and smoking);
- Medical history, physical and neurological exam, concomitant medications;
- Disease history (date/months since symptom onset, date/months since diagnosis, family history of neurologic disease) for cognitively impaired subjects;
- Ohio State University Traumatic Brain Injury Identification Method (OSU TBI-ID);
- Mini Mental State Exam (MMSE);
- Safety assessments: Vital signs (pulse rate, respiratory rate, supine blood pressure, height and weight), ECG, safety labs(hematology, chemistry, and urinalysis);
- Serum beta-hCG test (for females of childbearing potential defined as pre-menopausal or less than 2 years post-menopausal and not surgically sterile);
- MRI imaging including standard clinical sequences and volumetric MRI;
- A physician will see the patient during the screening visit.

Baseline assessments may be performed at the screening visit or +/- 30 days of the initial ¹⁸F-AV-1451 Imaging Visit. Raters administering the MMSE and baseline assessments described below will be blinded to the ¹⁸F-AV-1451 scans for subjects in the Confirmatory Cohort.

Baseline assessments will include:

- Alzheimer's Disease Assessment Scale- Cognitive subscale (ADAS-Cog11);
- Neuropsychological test battery (Digit Symbol Substitution Test (DSST), Digit span forward and backward ,Trail Making A and B, Logical Memory Test, Immediate and Delayed Recall Story A , Animal list generation, Boston Naming Test (BNT) (30 item), American National Adult Reading Test (ANART), Clock Drawing Test, Benton Judgment of Line Orientation test);
- Subjects in the Confirmatory Cohort will also be administered the Clinical Dementia Rating (CDR) Scale;
- Pfeffer Functional Activities Questionnaire (FAQ). For the MCI and AD groups only.

7.1.2. Optional Cerebrospinal fluid (CSF) collection by Lumbar Puncture (LP) (A β , p-tau, t-tau); Exploratory Phase only

Some subjects (depending on site participation) who are \geq 50 years of age who qualify for the study will be offered to consent for optional CSF collection by LP. The LP should be performed at least 48 hours apart from the PET imaging sessions and should be performed within +/- 60 days of the initial ¹⁸F-AV-1451 Imaging Visit. Each LP will be done by a qualified physician who is experienced in performing the procedure. Subjects,

or their designated decision maker, will call the investigator to report any adverse events associated with the LP procedure.

7.1.3. Initial PET Imaging Visits:

Subjects who qualify will have a florbetapir F 18 PET imaging session and their initial ¹⁸F-AV-1451 PET imaging session. The imaging sessions must be performed at least 48 hours apart, but not more than 60 days apart. The order of the scans is interchangeable.

Florbetapir F 18 PET Imaging Session

- For women of childbearing potential, a negative urine pregnancy test must be obtained within 24 hours prior to injection;
- A physician or physician designee must see the subject prior to administration of Florbetapir F 18 Injection to determine if they are still suitable to undergo the scan;
- Vital signs will be taken (pulse rate, respiratory rate, supine blood pressure, and weight) immediately prior to injection of florbetapir F 18;
- Subjects will receive a single IV bolus injection of approximately 370 MBq (10 mCi) +10% of florbetapir F 18 followed by a saline flush. A 10-minute(2 acquisitions of 5 minute duration) continuous, dynamic PET brain scan will begin approximately 50 minutes following the dose administration;
- A physician or physician designee will see the subject prior to discharge from the imaging center to evaluate the subject's readiness for discharge;
- A follow-up phone call to the subject, or designated decision maker, will be conducted between 2 or 3 business days of the imaging day, but not before 48 hours post-injection, to confirm subject well-being and to collect information about any new adverse events. If both of these days are not business days, the follow-up phone call can occur the following business day.

¹⁸F-AV-1451 PET Imaging Session: Raters administering the MMSE and baseline assessments will be blinded to the ¹⁸F-AV-1451 PET scan for subjects in the Confirmatory Cohort.

- A physician must see the subject prior to administration of ¹⁸F-AV-1451 Injection to determine if they are still suitable to undergo the scan;
- For women of childbearing potential, a negative urine pregnancy test must be obtained;
- Vital signs will be taken at the following time points:
 - immediately prior to administration of ¹⁸F-AV-1451 Injection
 - within 5 minutes after completion of injection of ¹⁸F- AV-1451 Injection
 - after completion of the PET scan, prior to discharge;
- ECGs will be taken at the following time points:

- Two will be taken approximately 5 minutes apart immediately prior to (within approximately 10 minutes) ¹⁸F-AV-1451 Injection administration
 - One will be taken within five minutes after completion of injection
 - One will be taken after completion of the PET scan, prior to discharge;
- Blood and urine samples will be collected for safety labs prior to administration of ¹⁸F-AV-1451 Injection and after completion of the PET scan prior to discharge;
- Blood will be collected for evaluation of ApoE genotype;
- Blood will be collected for storage and genetic analysis (participant may opt out) ;
- Subjects will receive a single IV bolus injection of approximately 370 MBq (10 mCi) +10% of ¹⁸F-AV-1451 Injection followed by a saline flush. At approximately 80 minutes post dose, a continuous 20-minute brain scan (4 acquisitions of 5 minute duration) will be obtained.);
- The injection site will be observed for excessive inflammation or damage to the surrounding tissue where the dose was injected;
- The subject will be requested to void after completion of the PET scan;
- Adverse events will be continuously monitored during the ¹⁸F-AV-1451 study imaging session; Subjects who experience an adverse event will not be discharged from the imaging center until the event has resolved or stabilized;
- A physician will see the subject prior to discharge from the imaging center to evaluate the subject's readiness for discharge; and
- A follow-up phone call to the subject, or designated decision maker, will be conducted between 2 or 3 business days of the imaging day, but not before 48 hours post-injection, to confirm subject well-being and to collect information about any new adverse events. If both of these days are not business days, the follow-up phone call can occur the following business day.

Longitudinal Visit Procedures

The longitudinal component will consist of the following sequence of activities:

7.1.4. First and Second Longitudinal Follow-up Visits

Exploratory Phase: The first and second follow-up visits will consist of PET scan procedures, an MRI, cognitive assessments and updated medical history and concomitant medications. The first follow-up scan will occur 9 (+/-2) months following the subject's initial ¹⁸F-AV-1451 scan. The second follow up scan will occur 18 (+/-2) months following the initial ¹⁸F-AV-1451 scan. The cognitive assessments and MRIs should be performed +/- 30 days of each corresponding ¹⁸F-AV-1451 PET imaging visit and within

the 9 (+/-2) months window. The cognitive assessments and MRI should take place in the same 30 day window.

Confirmatory Phase Cohort: The first and second follow-up visits will consist of cognitive assessments and updated medical history and concomitant medications. The first follow-up visit will occur 9 (+/-2) months following the subject's initial ¹⁸F-AV-1451 scan. The second follow-up visit will occur 18 (+/-2) months following the initial ¹⁸F-AV-1451 scan.

Cognitive Assessments: Raters administering the below assessments will be blinded to the ¹⁸F-AV-1451 scans for subjects in the Confirmatory Cohort

- Mini Mental State Exam (MMSE);
- Alzheimer's Disease Assessment Scale- Cognitive subscale (ADAS-Cog11);
- Neuropsychological test battery (Digit Symbol Substitution Test (DSST), Digit span forward and backward ,Trail Making A and B, Logical Memory Test, Immediate and Delayed Recall Story A , Animal list generation, Boston Naming Test (BNT) (30 item), American National Adult Reading Test (ANART), Clock Drawing Test, Benton Judgment of Line Orientation test);
- Clinical Dementia Rating (CDR) Scale; For the MCI and AD groups only.
- Pfeffer Functional Activities Questionnaire (FAQ). For the MCI and AD groups only.

Magnetic Resonance Imaging (MRI) (for Exploratory Phase cohort only)

MRI, including both volumetric and standard clinical sequences, will be obtained at the first and second follow-up visits.

¹⁸F-AV-1451 PET Imaging Session (for Exploratory Phase cohort only)

The first follow-up scan will occur 9 (+/-2) months following the subject's initial ¹⁸F-AV-1451 scan. The second follow up scan will occur 18 (+/-2) months following the initial ¹⁸F-AV-1451 scan. Procedures for the longitudinal follow-up scans will be identical to the initial scan:

- A physician must see the subject prior to administration of ¹⁸F-AV-1451 Injection to determine if they are still suitable to undergo the scan;
- Updated medical history and concomitant medications;
- For women of childbearing potential, a negative urine pregnancy test must be obtained;
- Vital signs will be taken at the following time points:
 - immediately prior to administration of ¹⁸F-AV-1451 Injection
 - within 5 minutes after completion of injection of ¹⁸F- AV-1451 Injection
 - after completion of the PET scan prior to discharge;
- ECGs will be taken at the following time points:

- Two will be taken approximately 5 minutes apart immediately prior to (within approximately 10 minutes) ¹⁸F-AV-1451 Injection administration
 - One will be taken within five minutes after completion of injection
 - One will be taken after completion of the PET scan prior to discharge;
- Blood and urine samples will be collected for safety labs prior to administration of ¹⁸F-AV-1451 Injection and after completion of the PET scan prior to discharge;
- Subjects will receive a single IV bolus injection of approximately (370 MBq) 10 mCi (+10%) of ¹⁸F-AV-1451 Injection followed by a saline flush. At approximately 80 minutes post dose, a continuous 20-minute brain scan (4 acquisition of 5-minute duration).
- The injection site will be observed for excessive inflammation or damage to the surrounding tissue where the dose was injected;
- The subject will be requested to void after completion of the PET scan;
- Adverse events will be continuously monitored during the ¹⁸F-AV-1451 study imaging session; Subjects who experience an adverse event will not be discharged from the imaging center until the event has resolved or stabilized;
- A physician will see the subject prior to discharge from the imaging center to evaluate the subject's readiness for discharge; and
- A follow-up phone call to the subject, or designated decision maker, will be conducted between 2 or 3 business days of the imaging day, but not before 48 hours post-injection, to confirm subject well-being and to collect information about any new adverse events. If both of these days are not business days, the follow-up phone call can occur the following business day.

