18F-AV-1451-A05 Protocol Amendment 2

An Open Label, Multicenter Study, Evaluating the Safety and Imaging Characteristics of 18F-AV-1451 in Cognitively Healthy Volunteers, Subjects With Mild Cognitive Impairment, and Subjects With Alzheimer's Disease

NCT02016560

Approval date: 07 Aug 2015

Protocol Number: ¹⁸F-AV-1451-A05

An open label, multicenter study, evaluating the safety and imaging characteristics of ¹⁸F-AV-1451 in cognitively healthy volunteers, subjects with Mild Cognitive Impairment, and subjects with Alzheimer's disease

Date and Version:

07 August 2015, Amendment 2

Name of Compound:

¹⁸F-AV-1451 ([F-18]T807)

Sponsor:

Avid Radiopharmaceuticals, Inc.
Philadelphia, Pennsylvania USA

Approvals/Signatures and Date:

CONFIDENTIAL

This material is the property of Avid Radiopharmaceuticals, Inc. (Avid). The information is confidential and is to be used only in connection with matters authorized by Avid and no part of it is to be disclosed to others without prior written permission from Avid.

Sponsor: Avid Radiopharmaceuticals, Inc.	Name of Compound: ¹⁸ F-AV-1451([F-18]T807)	Active Ingredient(s): 7-(6-[F-18]fluoropyridin-3-yl)-5H-pyrido[4,3-b]indole
Title of Study: ¹⁸ F-AV-1451-A05		
An open label, multicenter study, evaluating the safety and imaging characteristics of ¹⁸ F-AV-1451 in cognitively healthy volunteers, subjects with Mild Cognitive Impairment, and subjects with Alzheimer's disease		
Planned number of subjects (Enrolled): 380		
The first Phase of the study will be divided into three groups:		

 1. Cognitively healthy volunteer subjects 
 a. Approximately 20 subjects ≥ 20 to ≤ 40 years of age b. Approximately 60 subjects ≥ 50 years of age 2. Mild cognitive impairment (MCI) (n=80) 3. Alzheimer's disease (AD) subjects 
 a. Approximately 60 subjects with an MMSE ≥ 20 b. Approximately 10 subjects with an MMSE >10 and <20 		
The second Phase of the study will enroll:		

 4. Approximately 150 subjects with cognitive impairment (MCI or demented subjects with a suspected neurodegenerative cause) and an MMSE ≥ 20 and ≤ 27. For the purposes of ensuring a distribution of disease severity, a target of at least 1/3 of the enrolled subjects will have dementia. 		
Name of compound: ¹⁸ F-AV-1451(also known as [F-18]T807)		
Dose: 370 MBq (10 mCi)		
Route of Administration: Intravenous (IV) bolus		
Study Phase: II		

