- j. For women of childbearing potential, a negative urine pregnancy test must be obtained within 24 hours prior to florbetapir F 18 injection and within 24 hours prior to ¹⁸F-AV-1451 injection.
- k. Including CDR for subjects in the Confirmatory Cohort.
- l. CSF collection may occur after the subject has passed screening procedures for subjects in the Exploratory Cohort only
- m. A physician or physician designee

Longitudinal Component

Exploratory Phase Cohorts ONLY

Evaluations	5 Month Follow-up Phone Call	9 (+/-2) Months First Longitudinal Follow-up Visit	14 Month Follow-up Phone Call	18 (+/-2) Months, Second Longitudinal Follow-up Visit
Updated Medical History	X	X	X	X
Updated Concomitant Meds	X	X	X	X
ECG		X ⁿ		X ⁿ
Vital Signs		X ^o		X ^o
Safety Labs		X ^p		X ^p
Urine Pregnancy test ^q		X		X
MMSE		X		X
ADAS-Cog 11 ^r		X		X
Neuropsych battery, including CDR ^r		X		X
MRI of the brain ^r		X		X
PET Brain Scan		X		X
Follow-up Phone Call ^s		X		X
Evaluation by a physician		X		X
Adverse Events		X		X
Serious Adverse Events		X		X

The First and Second Longitudinal Follow-up Visits will be performed over several days.

- n. Two ECGs will be taken approximately 5 minutes apart immediately prior to (within approximately 10 minutes) ¹⁸F-AV-1451 Injection administration. One will be taken within 5 minutes after completion of injection. One will be obtained at the end of imaging day
- o. Vital signs include pulse rate, respiratory rate, supine blood pressure, temperature and weight
- p. Blood and urine samples will be collected prior to administration of ¹⁸F-AV-1451 Injection and at the end of the imaging day.
- q. For women of childbearing potential, a negative urine pregnancy test must be obtained within 24 hours prior to ¹⁸F-AV-1451 injection.
- r. ADAS-Cog 11, Neuropsych battery, and MRI can be performed +/- 30 days of the ¹⁸F-AV-1451 scan and within 30 days of each other. Assessments should be performed within the specified window of 9 (+/-2) months or 18 (+/-2) months.
- s. Between 2 or 3 business days of the imaging day

Confirmatory Phase Cohort ONLY

Evaluations	5 Month Follow-up Phone Call	9 (+/-2) Months, First Longitudinal Follow-up Visit	14 Month Follow-up Phone Call	18 (+/-2) Months, Second Longitudinal Follow-up Visit
Updated Medical History	X	X	X	X
Updated Concomitant Meds	X	X	X	X
MMSE		X		X
ADAS-Cog 11		X		X
Neuropsych battery, including CDR		X		X

INVESTIGATOR'S AGREEMENT TO PROTOCOL

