6.4.2.3.1 Clinical Meaningful Changes

Clinically meaningful changes will be defined by categorizing the change in psychometric scores, as follows:

1. a 3 point or more drop in MMSE relative to baseline;
2. a 4 point or more increase in ADAS Cog 11 relative to baseline;
3. a 3 point or more increase in FAQ relative to baseline ;
4. a 1 point or more increase in CDR SB relative to 9 month ;
5. a 12 point or more increase in ADAS+FAQ composite relative to baseline
6. CDR global score will be categorized as decreasing; stay the same; increasing from 9 month.

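### Protocol 7.1.1 and 7.1.4 tie FAQ, and 7.1.4 ties follow-up CDR, to the MCI and AD groups, which leaves out Confirmatory subjects with non-AD dementia and contradicts the Confirmatory flow chart on CDR

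*Protocol*

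**What the plan says.** **Scope in the text.** Protocol 7.1.4 has a single list of cognitive assessments for the 9- and 18-month visits of both phases; its lead-in mentions rater blinding for the Confirmatory Cohort. Two entries carry a diagnostic limit: "Clinical Dementia Rating (CDR) Scale; For the MCI and AD groups only" and "Pfeffer Functional Activities Questionnaire (FAQ). For the MCI and AD groups only". The baseline list in 7.1.1 limits FAQ in the same words. For CDR at baseline, 7.1.1 instead says: "Subjects in the Confirmatory Cohort will also be administered the Clinical Dementia Rating (CDR) Scale".

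**Who the groups are.** The synopsis introduces healthy volunteers, MCI and AD with "The first Phase of the study will be divided into three groups". The second-phase cohort is a separate fourth item. Its inclusion criteria (5.3.1) admit "MCI or dementia with a suspected neurodegenerative cause", with at least one third of about 150 subjects to have dementia.

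**Flow charts (11.2).** The Confirmatory follow-up chart marks "Neuropsych battery, including CDR" at 9 and 18 months with no diagnostic limit. The footnote to the battery row of the baseline chart reads "Including CDR for subjects in the Confirmatory Cohort". FAQ has no row or footnote in any Protocol chart or in the SAP copies. The neuropsychological battery as itemised in 7.1.1 and 7.1.4 does not contain FAQ.

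**Use of the scores.** SAP 6.4.2.3.1 gives six definitions of clinically meaningful change, among them "a 12 point or more increase in ADAS+FAQ composite relative to baseline". SAP section 3 restricts that plan to the exploratory phase. Protocol 8.1.1.2 and 8.1.4 leave the confirmatory endpoint open: a progression measure is to be picked as truth standard on the strength of the exploratory results.

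**The concern.** The limit makes sense in the Exploratory Phase, where the subjects outside MCI and AD are healthy volunteers. In the Confirmatory Cohort every subject is impaired and AD is not an entry requirement, so the same limit removes a set of patients defined by suspected cause of disease. A site that follows 7.1.4 as written would give such a patient a baseline CDR but no later one, and no FAQ at all. A site that follows the chart would give CDR throughout and would find no instruction on FAQ.

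If the truth standard chosen later uses FAQ or CDR, the outcome would be missing according to suspected aetiology and not at random. Scores not taken at a visit cannot be recovered. The choice of endpoint would then be narrowed in practice to what had been collected.

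**Working it through.** The documents give no figure for this point, so the check is a comparison of the passages, a count of exposed definitions, and the sample-size margin.

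**1. Text against chart, for a Confirmatory subject with non-AD dementia**

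| Score | Visit | Protocol 7.1.1 / 7.1.4 | Flow chart (11.2) |
|---|---|---|---|
| CDR | Baseline | Yes | Yes |
| CDR | 9 and 18 months | No | Yes |
| FAQ | Baseline | No | Not named |
| FAQ | 9 and 18 months | No | Not named |

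Text and chart conflict on follow-up CDR. For FAQ, the text excludes the subject and the chart does not name the score.

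**2. Definitions in SAP 6.4.2.3.1 that depend on these scores**

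| Definition | Score | Exposed if the chart governs CDR | Exposed if 7.1.4 governs CDR |
|---|---|---|---|
| 1 | MMSE | no | no |
| 2 | ADAS-Cog 11 | no | no |
| 3 | FAQ | yes | yes |
| 4 | CDR-SB, from month 9 | no | yes |
| 5 | ADAS+FAQ | yes | yes |
| 6 | CDR global, from month 9 | no | yes |
| **Total** | | **2 of 6** | **4 of 6** |

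**3. Sample-size margin.** Inputs from Protocol 8.1.1.2: 115 evaluable subjects needed, about 20% dropout, 150 enrolled. The plan's enrolment follows from 115 / 0.8 = 143.75, so 144, which the plan takes up to 150. Expected evaluable subjects: 150 × 0.8 = 120. Margin: 120 − 115 = 5. The 115 is taken as stated; how it was derived is a separate question.

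**4. Size of the gap.** At the one-third target, 150 / 3 = 50 subjects have dementia. Let f be the share of these with suspected non-AD disease. The documents do not give f, so it is an assumption. Subjects without the score: 50f. Evaluable subjects, with the same dropout in all: 0.8 × (150 − 50f).

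| f (assumed) | Enrolled without the score | Evaluable | Against 115 |
|---|---|---|---|
| 0 | 0 | 120 | +5 |
| 10% | 5 | 116 | +1 |
| 20% | 10 | 112 | −3 |
| 30% | 15 | 108 | −7 |

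The margin is gone when 0.8 × (150 − 50f) = 115, that is f = (150 − 143.75) / 50 = 0.125, or 12.5%.

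**5. Effect on accuracy measures.** SAP 8.6.2.4.4 uses a 2×2 table with A and B in the AD++ row and C and D in the other row. Sensitivity is A/(A+C) and specificity is D/(B+D). Suppose, as an illustration, that all missing subjects fall in the second row and that C and D shrink by the same factor k < 1. Sensitivity becomes A/(A+kC), which is higher; specificity becomes kD/(B+kD), which is lower; the negative predictive value D/(C+D) does not change. If the losses fall in the first row, sensitivity falls and specificity rises. Both measures can move, and the direction depends on a scan distribution that the documents do not give.

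**The case against.** The strongest reply is that the phrase was meant only to spare healthy volunteers. Protocol 5.1 describes the whole study as one of controls and patients with MCI and AD. Every Confirmatory subject must have a study partner who can report on daily activities, and 8.1.4 foresees hypotheses about functional as well as cognitive change. This is a plausible account of the intent, but no passage states it. Within the baseline list of 7.1.1, CDR is assigned to the Confirmatory Cohort by name and FAQ to the MCI and AD groups. For disease history, the same section uses a wider term covering all impaired subjects. Sites have to act on the wording.

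A reader might go further and infer that no Confirmatory subject belongs to those groups, so that FAQ is missing for all 150. The documents do not support that. The same reading would bar follow-up CDR for the whole cohort, although the cohort has CDR at baseline and its own chart schedules CDR later. Nor does the absent chart row prove that FAQ is not collected: the Exploratory charts lack the row too, yet the SAP lists and analyses FAQ at baseline and follow-up. The chart's battery row is also wider than the itemised list, since it includes CDR.

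Three further limits stand. Follow-up CDR is a contradiction to reconcile and not an established gap. The six definitions belong to an exploratory-phase SAP, and MMSE and ADAS-Cog 11 are unaffected. Definitions 4 and 6 start from month 9 because Exploratory subjects have no baseline CDR, so they would need adapting for the Confirmatory Cohort.

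The definitions remain relevant as candidates. The SAP repeats its diagnostic-performance analysis in MCI/AD subjects with MMSE 20-27 because that subset resembles the Confirmatory Cohort, and FAQ and ADAS+FAQ events are among those analysed.

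**Conclusion.** The concern holds as an inconsistency with a possible cost in outcome data. Read literally, 7.1.1 and 7.1.4 leave Confirmatory subjects with non-AD dementia without FAQ, and 7.1.4 leaves them without follow-up CDR; the Confirmatory chart says otherwise for CDR and is silent on FAQ. Two of the six candidate definitions are exposed if the chart governs CDR, and four if 7.1.4 governs.

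The consequence is conditional on three things: a FAQ- or CDR-based truth standard is chosen, sites follow the text literally, and an appreciable share of the demented subjects have suspected non-AD disease. At an assumed 10-30% of about 50, 5-15 enrolled subjects are affected and 116 to 108 remain evaluable, against 115 needed.

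A reader might also infer that the missing subjects would mostly have tau-negative scans, so that specificity and negative predictive value would be biased in a known direction. The documents do not say how non-AD dementias read on this scan, and sensitivity could move as well. What can be said is that missingness by suspected aetiology could distort both sensitivity and specificity.

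**What to change.** In Protocol 7.1.1 and 7.1.4, state that FAQ applies to the Exploratory MCI and AD groups and to all Confirmatory Cohort subjects. In 7.1.4, state the same for CDR at follow-up, so that the section agrees with the Confirmatory flow chart. Add an FAQ row to the flow charts at baseline, 9 and 18 months. Make the change before the truth standard is fixed and before further visits pass, since missed scores cannot be obtained later.

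The cost is a short clarifying amendment and, for some subjects, one more brief informant questionnaire per visit. The informant is already there, because a study partner is an entry requirement for every Confirmatory subject.
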